6.7 Missing or Incomplete Data

Missing data will not be imputed and only observed data will be included in the analysis.

7. Study Monitoring

7.1 Concomitant Medication/Supplements and Treatment

All concomitant medications/supplements used 30 d prior to Visit 1 (day -7) and during the study will be reported to the study personnel for assessment and recorded in the subject's eCRF.

Use of the medications/supplements described in the "Exclusion Criteria" section and Appendix 1 is not allowed during this study. If a subject requires any of these medications/supplements, the subject may not enter the study. If a subject uses any exclusionary medications/supplements once enrolled, a protocol deviation will be documented.

7.2 Compliance Monitoring

Compliance with the study product will be recorded in the subject's source document. Non-compliance will be witnessed by study staff and defined as not consuming the study product in its entirety at Visits 2, 3, and 4 (days 0, 7, and 14).

7.3 Adverse Event Monitoring

In a consensus view of guidelines for the design, conduct and reporting of human intervention studies to evaluate the health benefits of foods, an International Life Sciences Institute Europe Expert Group defines an AE as "any untoward medical occurrence or undesirable clinical experience in a participant in a clinical trial, whether or not considered related to the intervention" (Welch 2011). This includes any occurrence that is new in onset or aggravated in severity or frequency from the baseline condition, or abnormal results of diagnostic procedures (including laboratory test abnormalities where applicable). Therefore, clinical observations, including responses to the question, "Have there been in any changes in your health or medications since you were last asked?" will be collected at Visits 2 through 4. These observations will be reviewed for assessment of AE, including severity and potential relationship to the intervention as determined by the Clinical Investigator.

Events should be considered AEs if they:

- Result in discontinuation from the study,
- Require treatment or any other therapeutic intervention,
- Require further diagnostic evaluation (excluding a repetition of the same procedure to confirm the abnormality),
- Are associated with clinical signs or symptoms judged by the Clinical Investigator to have a significant clinical impact.

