Stratum $Plus^{TM}$, is a highly pure form of strontium L-lactate (the strontium salt of L-lactic acid). Stratum Plus is manufactured in compliance with current Good Manufacturing Practices. The product has been thoroughly tested and meets rigorous purity specifications. It is free from contamination by D-lactic acid and trace metals known to harm human health. Unlike strontium renalate (and other related strontium salts), no clinical trials have been conducted with Stratum Plus. Thus, this study will be conducted to obtain pharmacokinetic (PK) information following acute oral intakes of three doses of Stratum Plus in healthy adults.

3. Objectives

The objective of this clinical trial is to obtain PK information following acute oral intakes of three doses of Stratum Plus in healthy adults.

4. Study Sample Population

Subjects will be healthy men and women 18-65 years of age, inclusive, with a body mass index (BMI) 18.0 to 31.9 kg/m². Subjects must also exhibit a body weight >60 kg, inclusionary.

5. Study Design and Procedures

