Blood samples will be obtained via the indwelling venous catheter or venipuncture at t=3,4,5,6, and $8 \text{ h} \pm 5 \text{ min}$, where t=0 h is the start of study product consumption, for the PK analysis of serum strontium. Subjects will be administered a standard lunch (immediately following the t=6 h blood draw), a standard snack (immediately following the t=8 h blood draw) and a standard dinner (at t=10 h). Subjects will consume the meals/snack in their entirety within 30 min. Following the final blood draw at $t=12 \text{ h} \pm 5 \text{ min}$, AEs will be assessed. Subjects will be dispensed a blank/new 24-h Diet Record to record all food and beverage consumed the day prior to Visit 3 (day 7); as well as a copy of the completed 24-h Diet Record (from day -1) with instructions to replicate the same food and beverage intake as closely as possible the day prior to the subsequent visit. Study instructions will also be provided [(i.e., fasting compliance (10-14 h, water only) and avoidance of alcohol 3 d prior to the subsequent test visits].

At Visits 3 and 4 (days 7 and 14), subjects will return to the clinic for clinic visit procedures (i.e., vital signs; body weight; review inclusion and exclusion criteria for relevant changes, and concomitant medication/supplement use review). AEs will be

assessed and subjects will be queried about study instructions compliance. The 24-h Diet Record will be collected and study staff will review the 24-h Diet Record to compare food and beverage consumption to the day -1 recall for consistency. If the subject's food intake is not consistent from the 24-h Diet Record reviewed at Visit 2 (day 0), the study staff should contact the Project Manager before continuing the visit as the test visit may require rescheduling. Subjects will then crossover to the next sequential dose of study product [medium dose at Visit 3 (day 7) and high dose at Visit 4 (day 14)] and repeat the PK test described above for Visit 2.

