t = -1.0 h	 Arrive at clinic; Study instructions query; Clinic visit procedures (vitals and body weight); Enrollment (Visit 2; day 0 only); AE assessment; IV inserted (at least 5 min prior to first blood draw)
t = -0.25 h ± 10 min	Blood sample obtained;Additional sample stored
t = 0 h	 Administer assigned study product; Ad libitum water consumption allowed for remainder of visit
$t = 1$ and $2 h \pm 5$ min	Blood sample obtained;Additional sample stored
Immediately following the t = 2 h blood draw	 Administer standard breakfast (consumed in 30 min);
$t = 3, 4, 5, and 6 h \pm 5$ min	Blood sample obtained;Additional sample stored
Immediately following the t = 6 h blood draw	Administer standard lunch (consumed in 30 min)
$t = 8 \text{ h} \pm 5 \text{ min}$	Blood sample obtained;Additional sample stored
Immediately following the t = 8 h blood draw	Administer standard snack (consumed in 30 min)
t = 10 h ± 5 min	Administer standard dinner (consumed in 30 min)
t = 12 h ± 5 min	 Blood sample obtained; Additional sample stored; AE assessment (immediately upon completion of blood sampling); Review study instructions; dispense copy and blank 24-h Diet Record (Visit 2 and 3 only)

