6.6 Safety Analysis

Safety will be assessed by AEs reported by subjects, as well as assessment of vital signs and body weight.

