7.3.5 Electronic CRF Recording of Adverse Events

All AEs will be recorded on the AE eCRF page. For subjects who have an ongoing AE at their final study visit, a follow-up AE eCRF page will be completed after 30 d. All SAEs must be recorded on the AE and SAE eCRF page.

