7.3.6 Serious Adverse Event Follow-Up

For all ongoing SAEs occurring during the study, the Clinical Investigator must submit follow-up reports to Biofortis Innovation Services regarding the subject's subsequent course. All SAEs that are ongoing at the end of the study or upon discontinuation of the subject's participation must be followed until either:

- The event resolves, or
- The event/condition has stabilized (e.g., in the case of persistent impairment), or
- The event returns to baseline, if a baseline value is available, or
- The subject dies, or
- The event can be attributed to other than the study treatment, or to other than the study conduct.

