8.5 Withdrawal of Subjects from the Study

Subjects may be removed from the study for any of the following reasons:

- A subject requests discontinuation;
- The Clinical Investigator initiates removal for medical or compliance reasons;
- Occurrence of any AE or condition that could, in the Clinical Investigator's opinion, interfere with the evaluation of the treatment effect of the study product or put the subject at undue risk.

It is understood by all concerned that an excessive rate of withdrawals can render the study uninterpretable, therefore, unnecessary withdrawal of subjects should be avoided.

Confidential

Should a subject decide to withdraw, all efforts will be made to complete and report observations as thoroughly as possible. In the event that a subject is withdrawn from the study, the reason for the withdrawal will be documented in the eCRF. Prior to a subject's withdrawal from the study, an attempt will be made to conduct an early termination visit, which will include the clinic visit procedures and AE assessment.

9. Administrative Matters

All references to the Sponsor in this section include all designees e.g., Contract Research Organizations or Consultants acting on behalf of the Sponsor.

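### New adverse events are asked about for 6–13 days after the low and medium doses, but for only 12 hours after the high dose

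*Combined protocol and SAP*

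**What the plan says.** Section 7.3 has a standard question about changes in health or medication since the subject was last asked; the answers "will be collected at Visits 2 through 4". Footnote 14 of the flowchart (Section 5.3) places the AE inquiry at the beginning and end of study visits. The test-day schedule in Section 5.6.6 puts the closing one after the 12 h draw: "AE assessment (immediately upon completion of blood sampling").

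The dose order in Section 5.2 is the same for everyone: low at Visit 2, then "medium dose at Visit 3 (day 7) and high dose at Visit 4 (day 14"). Visit 4 is the last scheduled visit. Footnote 1 of Section 5.3 sets the washout between test visits at 6–13 d.

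Four provisions reach beyond a visit:

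- Section 7.3.5: "For subjects who have an ongoing AE at their final study visit, a follow-up AE eCRF page will be completed after 30 d".
- Section 7.3.6 requires follow-up of "All SAEs that are ongoing at the end of the study", or at a subject's discontinuation.
- Section 7.3.4 has serious events (SAEs) reported once the investigator becomes aware of them.
- Section 8.5, for subjects who withdraw: "an attempt will be made to conduct an early termination visit".

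Section 6.6 says "Safety will be assessed by AEs reported by subjects", together with vital signs and body weight. It does not say how events are assigned to a dose or tabulated.

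**The concern.** Because the question looks back to the previous query, the opening query at Visit 3 covers the whole interval after the low dose, and the opening query at Visit 4 covers the whole interval after the medium dose. Nothing plays that part for the high dose. A subject who feels well at 12 h and develops a non-serious event the next day is never asked about it.

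Vital signs and body weight follow the same pattern. On test days they are scheduled only at t = -1.0 h, before dosing. The Visit 3 and Visit 4 readings therefore also serve as late readings after the low and medium doses, while none is scheduled after the high dose.

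This matters because the protocol states in its background section that "no clinical trials have been conducted with Stratum Plus". The dose with least reassurance from the rest of the study gets the shortest solicited observation. If AEs are later listed by dose, a short list at the high dose could be taken for good tolerability when it partly reflects a shorter period of asking.

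**Working it through.** The plan gives no figure for the length of AE observation, so there is none to reproduce. The check compares the solicited windows, taken as the time from dosing to the last scheduled query that would pick up a new event.

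**Inputs.** Washout 6–13 d (Section 5.3, footnote 1); nominal dosing days 0, 7 and 14 (Section 5.2); last query after the high dose at 12 h (Section 5.6.6); 10 subjects to be enrolled, with a goal of at least 6 completing (Section 6.2).

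**Window length**, reading the washout as the interval from dose to dose:

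| Interval | Low or medium dose | High dose | Ratio |
|---|---|---|---|
| 6 d | 6 × 24 = 144 h | 12 h | 144/12 = 12 |
| 7 d (nominal) | 7 × 24 = 168 h | 12 h | 168/12 = 14 |
| 13 d | 13 × 24 = 312 h | 12 h | 312/12 = 26 |

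Ending the window at the arrival query (t = -1 h) gives 143, 167 and 311 h, and ratios of 11.9, 13.9 and 25.9. If the washout instead counts only the full days between visits, doses are 7–14 d apart (168–336 h) and the ratio is 14 to 28.

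**Subject-days = n × hours / 24.**

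- n = 10: high dose 10 × 12/24 = 5; each lower dose 10 × 144/24 = 60 to 10 × 312/24 = 130.
- n = 6: high dose 6 × 12/24 = 3; each lower dose 6 × 144/24 = 36 to 6 × 312/24 = 78.

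**Background events at a constant rate.** The expected solicited count is proportional to subject-days, so the high-dose count relative to each lower dose is 5/60 = 8.3% at 6 d, 5/70 = 7.1% at 7 d and 5/130 = 3.8% at 13 d. The ratio does not depend on n if all subjects receive all doses.

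**Product-related events.** The documents give no onset times. As an assumption for illustration only, let onset be exponential with mean m, so that the share starting inside the window is 1 − exp(−window/m):

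| Assumed mean onset m | High dose, 12 h |
|---|---|
| 4 h | 1 − exp(−3) = 95% |
| 6 h | 1 − exp(−2) = 86% |
| 12 h | 1 − exp(−1) = 63% |
| 24 h | 1 − exp(−0.5) = 39% |
| 48 h | 1 − exp(−0.25) = 22% |

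At the lower doses with m = 48 h, the share is 1 − exp(−144/48) = 95% at 6 d and 1 − exp(−312/48) = 99.8% at 13 d; a shorter mean gives more. These are shares of events that start while the window is open. They assume complete recall at the next visit, so they are upper limits on what would be recorded.

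**Do the other provisions close the gap?** The 30-d page needs an event already present at the final visit. SAE follow-up needs an SAE already ongoing. SAE reporting needs the investigator to hear of the event by some other route. The early termination visit is for withdrawals. None of them asks a completer about a new non-serious event that starts more than 12 h after the high dose.

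**The case against.** The strongest reply is that this is a pharmacokinetic study. Its objective and every listed outcome are pharmacokinetic, the analysis is descriptive, and Section 6.6 plans no AE comparison between doses. All three doses share the same 12 h in-clinic window with a closing query, so a like-for-like comparison is already possible. The longer windows at the lower doses are a by-product of the next dosing visit. Section 2 also reports that strontium salts have been given safely at up to 2 g a day for up to three years, and each dose here is a single intake. The 4–8% figure concerns events the product does not cause, and the onset table rests on assumed means. Finally, the consent pages are not available for review, so any instruction to report later events cannot be checked.

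Much of this stands, and it limits the size of the claim. No planned analysis is invalidated, and the number of product-related events lost is unknown. The by-dose point applies only if someone makes that reading. With 10 subjects, a fixed order and no control, equal windows would not turn the study into a dose-response safety test.

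It does not remove the gap. The Section 2 experience concerns other strontium salts, and the text does not say whether 2 g refers to salt or to strontium. The plan itself does not treat exposure as finished at 12 h: it requires at least a 6-d washout and extrapolates the area under the curve to infinity. An instruction to report spontaneously, if one exists, is not the same as asking.

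**Conclusion.** The concern holds. As written, new AEs are solicited for 144–312 h after each lower dose and for 12 h after the high dose, 12 to 26 times shorter (14 to 28 if the washout counts full days between visits). No reading of the washout makes the windows equal.

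The schedule fact is certain on the text; the consequence is less so. The 4–8% figure assumes only a constant background rate. The loss of product-related events depends on onset times that the documents do not give: it is small if onset is within a few hours and large if onset averages a day or more. The pharmacokinetic objective is unaffected. This is a gap in safety ascertainment at the highest dose, worth closing because it is cheap to close.

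**What to change.** 1. Add one AE query, using the existing question, 6–13 d after Visit 4, for example by telephone, and enter it in Sections 5.3 and 7.3.
2. In Section 6.6, state that any by-dose AE summary will show events with onset 0–12 h after dosing separately from those with onset between 12 h and the next contact.
3. If the query is not added, limit any by-dose comparison to onset 0–12 h and state that later events after the high dose were not solicited.

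**Cost.** The query means about 10 calls, and each subject's participation ends 6–13 d later. If the protocol is already approved, Section 9.1 requires a signed amendment and a revised consent form, with IRB approval. A telephone query differs in mode from the clinic query, so ascertainment would be closer but not identical, and it would not supply vital signs or body weight. Items 2 and 3 need a sentence or two in Section 6.6 and the AE onset time. The recording text in Sections 7.3.1, 7.3.2 and 7.3.5 does not mention onset time, so the AE page should be checked for that field.

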7.3.1 Grading and Severity

The Clinical Investigator will evaluate all AEs with respect to their severity, and record the outcome and action taken on the AE eCRF. AEs will be graded as:

Mild:

Awareness of symptoms but easily tolerated

Moderate:

Discomfort enough to interfere with but not prevent daily activity

Severe:

Unable to perform usual activity

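### Section 7.3 does not say whether its four-item list is a threshold for an adverse event or only examples, so untreated mild symptoms may go unrecorded

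*Combined protocol and SAP*

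**What the plan says.** Section 7.3 takes its AE definition from an expert-group guideline: "any untoward medical occurrence or undesirable clinical experience in a participant in a clinical trial, whether or not considered related to the intervention". It widens this at once: "This includes any occurrence that is new in onset or aggravated in severity or frequency from the baseline condition". Neither sentence sets a minimum severity. The section then says that observations collected at Visits 2 to 4 will be reviewed to assess AEs.

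Directly after that comes "Events should be considered AEs if they" and four bullets. The first two are "Result in discontinuation from the study" and "Require treatment or any other therapeutic intervention". The third is a need for further diagnostic evaluation, not counting a repeat test done to confirm an abnormal finding. The fourth is association with signs or symptoms "judged by the Clinical Investigator to have a significant clinical impact".

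Section 7.3.1 grades AEs starting from Mild, described as "Awareness of symptoms but easily tolerated". Section 7.3.5 sends all AEs to the AE page of the eCRF. Section 6.6 begins "Safety will be assessed by AEs reported by subjects" and goes on to name vital signs and body weight as well.

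**The concern.** The definition and the list give different answers for the same ordinary event. The list follows the sentence on reviewing observations, so staff can reasonably take it as the test to apply in that review. An event that fails the test would not reach the eCRF, the severity grading in 7.3.1, the relatedness judgment in 7.3.2 or the 30-day follow-up of ongoing AEs in 7.3.5.

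At stake is the completeness of the tolerability record. Section 2 states that the product has had no clinical trials. In a single-dose study of healthy adults, short and easily tolerated symptoms are a large part of what such a record can be expected to show.

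**Working it through.** No figure in the plan bears on this point, so the check is mainly textual.

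**Step 1. One event against each rule.** Take a symptom that starts after dosing, is easily tolerated, is not treated, leads to no further evaluation, and does not stop the subject from continuing.

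| Rule | Does the event qualify? |
|---|---|
| Definition in 7.3 (untoward or newly occurring) | Yes |
| Mild grade in 7.3.1 | Yes |
| Criterion 1, discontinuation | No |
| Criterion 2, treatment | No |
| Criterion 3, further diagnostic work | No |
| Criterion 4, clinical impact | Generally no; left to the investigator |

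A mild symptom that is treated or worked up would meet criterion 2 or 3, so the gap concerns only those that are not. Section 5.4.3 makes criterion 2 harder to reach: subjects are asked to refrain from over-the-counter medicines, and from prescription medicines other than stable oral contraceptives, throughout the study.

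**Step 2. Does any text settle which rule governs?** None does. The lead-in says *if*, not *only if*. It does not say whether one criterion or all must be met. It refers to events in general and does not limit the list to test results.

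**Step 3. What else would capture safety after a dose?**
- The test-day schedule in 5.6.6 puts vital signs and body weight at t = -1.0 h, before dosing, at Visits 2, 3 and 4.
- After the low and medium doses, the next vital signs come at the following visit, after a washout of 6 to 13 days (5.3, footnote 1).
- After the high dose at Visit 4, no further vital signs, weight or visit is scheduled.
- The chemistry and hematology panels are done at screening only (5.3).
- The AE assessment is repeated after the 12 h blood draw at each test visit (5.6.6). It is the only safety measure scheduled in the hours after a dose.

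**Step 4. Illustration of scale.** Let *q* be the share of subjects with an untreated mild symptom at a given dose. The plan gives no value, so 10%, 20% and 30% are assumptions. With *n* subjects, the chance that at least one has such a symptom is 1 − (1 − *q*)^*n*. Section 6.2 gives *n* = 10 enrolled and a minimum of 6 completers.

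| *q* (assumed) | *n* = 10 | *n* = 6 |
|---|---|---|
| 10% | 1 − 0.9^10 = 65.1% | 1 − 0.9^6 = 46.9% |
| 20% | 1 − 0.8^10 = 89.3% | 1 − 0.8^6 = 73.8% |
| 30% | 1 − 0.7^10 = 97.2% | 1 − 0.7^6 = 88.2% |

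Under the definition these cases would be recorded. Under the list used strictly as a threshold, none would be. That 0% follows from the threshold reading itself and is not an estimate of what staff would do.

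**The case against.** The best case for the plan is that the list is inclusive. *If* is not *only if*. The broad definition, the Mild grade and the rule that all AEs go on the eCRF all suggest that mild events were meant to be captured, and a threshold reading would leave the Mild grade largely empty. Symptoms are also actively sought, by an open-ended question at the start and end of visits (5.3, footnote 14). This stands as evidence of intent, and it places the risk in classifying events, not in asking about them. It does not remove the ambiguity: read as examples, the list adds nothing to the definition, and nothing tells staff to read it that way.

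A second defence is that the list was written for abnormal findings, as the third criterion's mention of confirming an abnormality suggests. Vital signs and capillary glucose at test visits could produce such findings. This is plausible, and it supports the fix below, but the text says events without that limit.

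A reader might infer three stronger points that the documents do not support:
- *AEs are the only safety information used.* Section 6.6 also names vital signs and body weight. The point is their timing.
- *No mild symptom can qualify.* One that is treated or worked up does.
- *A comparison between doses is distorted.* The fourth criterion does rest on an investigator who knows the dose, but no between-dose AE comparison is planned, and the fixed low, medium, high order already ties dose to visit.

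**Conclusion.** The point holds as an unresolved conflict between two rules in section 7.3. It affects mild symptoms that are untreated, not worked up and do not lead to withdrawal. Whether any would be lost depends on how staff read the list, and the documents give no basis for estimating that. The incidence figures show only that such symptoms could well occur in 6 to 10 subjects if the assumed rates were near the truth. The wording should be settled because the list helps decide what enters the only safety measure scheduled soon after dosing, in the product's first clinical study. It is not evidence that the plan intends to discard mild events.

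**What to change.** Make two changes in section 7.3.

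1. State that every new or worsened sign or symptom is recorded as an AE, whatever its severity or need for treatment, and is then graded under 7.3.1 and 7.3.2.
2. Reword the lead-in so that the four-item list applies only to abnormal laboratory, vital-sign or other diagnostic findings.

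The cost is two sentences, a few more mild entries on the eCRF, and a slightly less favourable-looking AE table. No assessment, visit or aspect of clinical management changes.
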